5. STUDY PARTICIPANTS

5.1. Disposition of Participants

A table of frequency counts and percentages of all participants who are enrolled, distributed study medication, and included in each analysis set will be provided. Participant disposition including study completion status and reasons for early termination will be tabulated overall. A by-participant listing will be provided.

5.2. Protocol Deviations

Two separate by-participant listings for major and minor protocol deviations will be provided.

5.3. Demographic

Descriptive statistics will be used to summarize the demographic characteristics (age, gender, race, ethnicity, height, weight, and BMI) overall using the Safety Set. A by-participant listing will also be provided.

5.4. Baseline Characteristics

The results of the following assessments completed during the baseline PSG will be summarized overall using the Safety Set:

- AHI(4%)
- ODI(4%)
- HB(4%)
- Total time with $\text{SaO}_2 < 90\%$

- Snoring index
- Arousal indices (respiratory and spontaneous)
- Fraction of hypopneas
- WASO
- Sleep stage (N1, N2, N3, R) separately in minutes and percent of total sleep time
- Sleep efficiency
- Number of awakenings
- Sleep onset latency
- Heart rate
- Total sleep time
- Systolic blood pressure
- Diastolic blood pressure

The baseline PSG parameters and vital signs will be included in their respective general listings.

5.5. Medical History

All medical conditions and surgical procedures will be coded using the Medical Dictionary for Regulatory Activities (MedDRA) version 23.0. The number and percent of participants with each medical condition and surgical procedure will be presented by MedDRA system organ class (SOC), preferred term (PT) overall for the Safety Set. Each participant will be counted only once per SOC and PT. A by-participant listing will also be provided.

5.6. Prior and Concomitant Medications

Prior and concomitant medications will be coded using September 2020 B3 Global World Health Organization (WHO) Drug Dictionary version. The number and percent of participants using each medication will be tabulated by Anatomical Therapeutic Chemical (ATC) level 3, preferred name overall. Each prior or concomitant medication reported more than one time will only be counted once per participant for each ATC level and preferred name. A by-participant listing will also be provided.

6. EFFICACY ANALYSIS

The mITT Set will be used for all efficacy analyses.

6.1. Primary Efficacy Analysis – HB(4%)

Multiple comparisons will be performed as described in Section 4.5. A repeated measures model (see Section 4.7) will be used to model change in $\log_{10}(\text{HB}[4\%] + 1)$ from baseline. Model based LS mean estimates will be provided for the following:

- mean change by study treatment (75/2.5 dose, 37.5/2.5 dose, placebo),

- difference in mean change between study treatments¹ (75/2.5 dose vs placebo, 37.5/2.5 dose vs placebo, and 75/2.5 dose vs 37.5/2.5 dose) with 95% confidence intervals and respective p-values (for null hypothesis).

If the model shows there is a visit (i.e., period) effect, then ad hoc analyses will be performed. A sensitivity analysis will be performed using the PP Set on the primary efficacy endpoint using the same methods described above and using HB(4%) with identity transform (i.e., without transform) on the mITT set.

Descriptive statistics for the reported value and change from baseline in $\log_{10}(\text{HB}[4\%] + 1)$ will be presented by study treatment. By taking the inverse transformations of the respective means, the geometric mean of HB(4%) + 1 and the ratio of the geometric mean to baseline will be reported.

6.2. Secondary Efficacy Analysis

6.2.1. HB(4%)

The secondary outcomes of 37.5/2.5 dose vs placebo and vs. 75/2.5 dose are described in the primary efficacy analysis for $\log_{10}(\text{HB}[4\%] + 1)$.

6.2.2. AHI(4%)

Multiple comparisons will be performed as described in Section 4.5. A repeated measures model (see Section 4.7) will be used to model change in AHI(4%) from baseline. Model based LS mean estimates will be provided for the following:

- mean change by study treatment (75/2.5 dose, 37.5/2.5 dose, placebo),
- difference in mean change between study treatments (75/2.5 dose vs placebo, 37.5/2.5 dose vs placebo, and 75/2.5 dose vs 37.5/2.5 dose) with 95% confidence intervals and respective p-values (for null hypothesis).

Descriptive statistics for the reported value and change from baseline in AHI(4%) will be presented by study treatment.

6.2.3. ODI(4%)

Multiple comparisons will be performed as described in Section 4.5. A repeated measures model (see Section 4.7) will be used to model change in ODI(4%) from baseline. Model based LS mean estimates will be provided for the following:

- mean change by study treatment (75/2.5 dose, 37.5/2.5 dose, placebo),
- difference in mean change between study treatments (75/2.5 dose vs placebo, 37.5/2.5 dose vs placebo, and 75/2.5 dose vs 37.5/2.5 dose) with 95% confidence intervals and respective p-values (for null hypothesis).

Descriptive statistics for the reported value and change from baseline in ODI(4%) will be presented by study treatment.

¹ Only 75/2.5 dose vs placebo is part of the primary outcome. The 37.5/2.5 dose vs placebo and 37.5/2.5 dose vs 75/2.5 dose are secondary outcomes.

6.2.4. Total time with SaO₂<90%

Multiple comparisons will be performed as described in Section 4.5. A repeated measures model (see Section 4.7) will be used to model total time with SaO₂<90%. Model based LS mean estimates will be provided for the following:

- mean change by study treatment (75/2.5 dose, 37.5/2.5 dose, placebo),
- difference in mean change between study treatments (75/2.5 dose vs placebo, 37.5/2.5 dose vs placebo, and 75/2.5 dose vs 37.5/2.5 dose) with 95% confidence intervals and respective p-values (for null hypothesis).

Descriptive statistics for the reported value and change from baseline in total time with SaO₂<90% will be presented by study treatment.

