2.2.3 Biological Rationale

AD109 is a new fixed dose drug combination of atomoxetine and R-oxybutynin being developed for OSA. Atomoxetine is a pre-synaptic norepinephrine reuptake inhibitor indicated for the treatment of attention deficit hyperactivity disorder in children and adults. R-oxybutynin has never been marketed, but racemic oxybutynin is approved as an antispasmodic drug that inhibits the muscarinic action of acetylcholine on smooth muscle and is indicated for the treatment of symptoms of bladder instability associated with voiding in patients with uninhibited neurogenic or reflex neurogenic bladder such as urgency, frequency, urinary leakage, urge incontinence and dysuria.

Efficacy of oxybutynin in overactive bladder may result both from antimuscarinic effects of oxybutynin and smooth muscle spasmolytic effects. The contribution to efficacy of oxybutynin in OSA is believed to be related to antimuscarinic effects, whereas spasmolytic effects may lead to effects on the bladder that are undesirable in typical OSA patients. The R-enantiomer of oxybutynin has been shown to confer the antimuscarinic effect of oxybutynin, whereas the spasmolytic effects (and other effects on calcium channel antagonism and local anesthetic effects) are non-stereoselective properties of both the enantiomers. Apnimed therefore believes that the combination of the R-enantiomer of oxybutynin with atomoxetine may have an improved safety and efficacy profile in OSA compared to the combination with the racemate of oxybutynin.

3 Endpoints

	Endpoints
Primary	Change in Hypoxic Burden (HB) 4% (scored in reference to AHI 4%), 75/2.5 dose vs. placebo
Secondary	 Change in HB 4%, 37.5/2.5 dose vs. placebo and vs. 75.2.5 Change in Apnea Hypopnea Index (AHI) 4% Change in Oxygen Desaturation Index (ODI) Total time with SaO₂ <90%, PSG nights Proportion of participants with ≥50% reduction, AHI, HB and ODI
Exploratory	 Karolinska sleepiness scale Sleep Quality VAS AHI 3% (hypopnea scored when associated with 3% O₂ desaturation or arousal) OSA endotypes endpoints (Vpassive, Vactive, Muscle Compensation, Loop Gain) PSG sleep and arousal parameters
Safety Endpoints	 Physical exam, vital signs, clinical laboratory assessment Spontaneous adverse events, including the post-dosing period DSST PSG parameters: heart rate, ECG, EEG, oximetry

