8.1 Sample Size Determination

A total of 30 patients will enter the 3-treatment crossover study. The study will have 80% power to detect a treatment difference on the primary endpoint at a two-sided 0.05 significance level, if the true difference between treatments on HB is at least -3.7 %min/h. This assumes that the within-subject standard deviation is 9 and a discontinuation rate of less than 20%.

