4.4.1. PSG Parameters

The criteria for use of PSG data will be as follows:

- When TST is < 120 minutes, only TST, time in bed, Stage N1%, Stage N2%, Stage N3%, and Stage R% will be reported. All other PSG indices will be excluded.
- Any AHI and HB parameters during REM will be reported only when the time spent in REM is > 5 minutes.
- Any AHI and ODI parameters in supine position will be reported only when the time spent supine is > 5 minutes.

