4.7. Modeling for Select Endpoints

In Section 6, modeling will be used for comparisons between study treatments with respect to given endpoints using the PROC GLIMMIX procedure in SAS. The model will include study treatment and visit as fixed effects. Within participant variability (nested within treatment sequence) will be modeled using an unstructured (e.g., TYPE = UN, CHOL) covariance pattern. The unstructured covariance parametrized through its Cholesky root is to be used for logistic regression models and models in which convergence fails for the completely unstructured covariance. Point (e.g., mean, difference of means) and inferential (e.g., confidence interval, p-values) statistics will be provided using least squares (LS) methods. Unless otherwise stated, the link will be identity and the distribution gaussian.

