7.6. PSG Parameters

PSG safety data will be summarized by presenting descriptive statistics of actual values and changes from baseline by study treatment. PSG safety parameters include total sleep time, heart rate, and total time with $\text{SaO}_2 < 90\%$. A by-participant listing of PSG parameters (including baseline and efficacy parameters) will also be provided.

² In the case that the total correct is 0, the participant will be dropped from the model.

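### Time with SaO₂<90% is analysed only as an unscaled total, so a treatment difference in sleep time would shift it even if oxygenation per hour of sleep were unchanged

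*SAP*

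**What the plan says.** Protocol Section 3 lists the secondary endpoint as "Total time with SaO₂ <90%, PSG nights". SAP 2.2.2 repeats it for efficacy, and SAP 2.2.4 lists it again among the PSG safety parameters.

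- **Efficacy (SAP 6.2.4):** "A repeated measures model (see Section 4.7) will be used to model total time with" SaO₂ below 90%. No transformation is named, so the SAP 4.7 default of an identity link and Gaussian distribution applies.
- **Model (SAP 4.7):** "The model will include study treatment and visit as fixed effects". Sleep time is neither a covariate nor an offset.
- **Safety (SAP 7.6):** "PSG safety parameters include total sleep time, heart rate, and total time with" SaO₂ below 90%. The method is descriptive: "PSG safety data will be summarized by presenting descriptive statistics of actual values and changes from baseline by study treatment". TST stands beside the total as a separate parameter, and the two are not combined.
- **Sleep-time rule (SAP 4.4.1):** "When TST is < 120 minutes, only TST, time in bed, Stage N1%, Stage N2%, Stage N3%, and Stage R% will be reported". This drops very short nights and makes no adjustment at or above 120 minutes.

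The other oxygenation and event endpoints are scaled. Protocol 8.1 sizes the trial on hypoxic burden in per-hour units ("if the true difference between treatments on HB is at least -3.7 %min/h"), and AHI and ODI are indices. SAP 6.3.3 also adds percentage of time supine as a covariate in one AHI analysis.

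**The concern.** Protocol 7.1.1 fixes time in bed at 8 hours, but not the time slept within it. Protocol 2.2.1 describes the airway collapse of sleep apnea as happening during sleep, so time below 90% should build up mainly while the participant is asleep. The total therefore mixes two quantities: how poor oxygenation is per unit of sleep, and how much sleep there was. Only the first is the intended effect.

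If a dose changes sleep time, the difference from placebo carries that change. As an efficacy endpoint, the total could overstate or understate benefit. As a safety parameter it matters more, because worse oxygenation per hour of sleep could be offset by fewer hours of sleep and show as no change.

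**Working it through.** The documents give no figure for time with SaO₂<90%, so there is no stated number to reproduce.

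**Inputs from the documents.** The total has no denominator (SAP 6.2.4, 7.6); the fixed effects are treatment and visit (SAP 4.7); time in bed is 480 minutes (Protocol 7.1.1); 30 participants enter, or 24 after 20% discontinuation (Protocol 8.1).

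**Assumptions.** The documents give neither TST, nor sleep lost or gained on drug, nor the share of sleep below 90%, nor the variance of the endpoint. I take the unit as minutes, a central placebo TST of 390 minutes (range 360 to 440), and a loss of 15 to 60 minutes.

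**1. Spurious change with equal oxygenation.** Let T = f × S, where f is the share of sleep below 90% and S is sleep time. With the same f on both nights and L minutes of sleep lost:

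relative change in T = [f(S − L) − fS] / fS = −L/S

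- S = 390, L = 30: 30/390 = 7.7% fall.
- S = 390, L = 60: 60/390 = 15.4% fall.
- Across the range: 15/440 = 3.4% to 60/360 = 16.7%.

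If sleep lengthens by the same amounts, the sign reverses. In minutes the artefact is f × L: for L = 60 it is 0.6, 3.0 or 6.0 minutes when f is 1%, 5% or 10%.

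**2. Masking in the safety role.** The total shows no change when f₁(S − L) = f₀S, that is, when the share of sleep below 90% has risen by L/(S − L).

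- S = 390, L = 30: 30/360 = 8.3% hidden rise.
- S = 390, L = 60: 60/330 = 18.2% hidden rise.

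**3. After division by TST.** T/S = f, so the spurious difference is 0 in every case in step 1, and the rises in step 2 appear in full.

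**4. Effect on the nominal test.** This was simulated on the planned untransformed scale with no true drug effect. Assumptions: 27 participants; lognormal share of sleep below 90% with median 1%, between-person ln-SD 1.4 and within-person ln-SD 0.7; night-to-night TST SD 40 minutes; paired test; 20,000 runs.

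| Sleep lost | Two-sided rejection at 0.05 |
|---|---|
| 0 min | 2.5% |
| 30 min | 3.1% |
| 60 min | 4.7% |

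The tail favouring the drug rises from 1.2% to 4.4% between 0 and 60 minutes lost, so the shift is directional, but total rejection stays under 5%.

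The result depends on the assumed spread. With a paired t-test, n = 30 and nominal 2.5% in that tail, the chance of p<0.05 in the drug's favour is:

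| SD of paired difference / placebo mean | 7.5% artefact | 15% artefact |
|---|---|---|
| 0.25 | 0.36 | 0.89 |
| 0.5 | 0.12 | 0.36 |
| 1.0 | 0.06 | 0.12 |
| 2.0 | 0.04 | 0.06 |

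The lognormal assumptions imply a ratio of about 2 to 3, near the bottom row. None of these ratios comes from the documents.

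**The case against.** **The direction is unknown.** A reader might infer that the endpoint favours the drug, or that sleep time is monitored because the drug shortens it. The documents support neither. Protocol 7.2 says only that sleep parameters will be monitored by PSG, gives no such reason, and notes that both components may be associated with somnolence. This objection stands: the bias is conditional, and its sign is open.

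**Type I error.** A reader might also infer an inflated false-positive rate. Under the same share assumptions, a log10(x+1) analysis gives about 8% and 13% for losses of 30 and 60 minutes. The SAP plans that transformation for hypoxic burden, not for this endpoint. On the planned scale, with those variances, rejection stays under 5%. Much higher rates need a far smaller SD than those variances imply. The point should not rest on alpha.

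**Extreme nights.** The 120-minute rule would admit nights of 121 and 450 minutes, a ratio of 3.7. That compares two hypothetical nights, not treatment means. The design is within-person, time in bed and lights-out are held constant, and Protocol 5.2 excludes typical sleep under 5 hours. Total time per 8-hour night is therefore a coherent quantity, and the ratio is not a fair measure of the problem.

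**Limited consequence.** SAP 6.2.4 points to SAP 4.5, but the endpoint is not among the nine ordered tests there. The safety summary is descriptive, TST is tabulated beside it, and SAP 6.3.3 reports sleep efficiency and wake after sleep onset by treatment. A reader could notice lost sleep. That reduces the harm but does not remove it, because separate summaries do not give the within-participant ratio.

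**Replacing the endpoint goes too far.** The protocol defines it as total time, so a substitution in the SAP alone would put the two documents at odds. That is right, and it limits the remedy to an addition.

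**Conclusion.** The point holds as a conditional bias in one nominally tested secondary endpoint and one descriptive safety parameter. The text is clear that the total is unscaled in both roles and that the model does not account for sleep time. If treatments differ in TST, the difference in total time is shifted by roughly the proportional difference in sleep: about 8% or 15% for 30 or 60 minutes of 390, in either direction. In the safety role, a rise of about 8% or 18% in the share of sleep below 90% could go unseen.

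These sizes rest on assumed sleep times and on desaturation occurring mainly in sleep. Sleep that contained no time below 90% could be lost without effect, and nights with TST under 120 minutes are excluded rather than scored as better. The documents do not say whether wake time within the 8 hours counts towards the total; if it does, the effect remains so long as desaturation is mostly in sleep. The primary conclusion on hypoxic burden is unaffected. This is a cheap improvement to the SAP.

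**What to change.** In SAP 6.2.4 and 7.6, keep the protocol-defined total time and add:

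- **Derivation:** percentage of TST with SaO₂<90% = (time below 90% during sleep / TST) × 100, stating that only time scored as sleep counts.
- **Efficacy:** the percentage run through the same SAP 4.7 model as the total.
- **Safety:** the percentage summarised by treatment beside the total and TST.
- **Interpretation:** any statement that oxygenation improved or was not harmed rests on the percentage as well as the total.

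The cost is one derivation and one table row from PSG data already collected, with no change to conduct, sample size or the protocol endpoint. The percentage does not correct for a changed mix of sleep stages or body position.

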6.2.5. Proportion of participants with $\geq 50\%$ reduction

Three separate repeated measures models (see section 4.7) will be used to model the probability of a $\geq 50\%$ reduction in AHI(4%), hypoxic burden, and ODI(4%) values respectively. A logit link with binomial distribution will be employed. For each of the three endpoints, model based LS mean estimates will be provided for the following:

- odds ratios for a $\geq 50\%$ reduction between study treatments (75/2.5 dose vs placebo, 37.5/2.5 dose vs placebo, and 75/2.5 dose vs 37.5/2.5 dose) with 95% confidence intervals and respective p-values (for null hypothesis).

The proportion, with 95% CI, of participants with $\geq 50\%$ reduction in AHI(4%), HB(4%), and ODI(4%) will be presented by study treatment in the same table as the models.

6.3. Tertiary Efficacy Analyses

6.3.1. KSS

Two separate repeated measure models (see section 4.7) will be used to model the probability of being alert (KSS score ≤ 3) and of not being sleepy (KSS score ≤ 5). A logit link with binomial distribution will be employed. For each of the two endpoints, model-based LS mean estimates will be provided for the following:

- odds ratios between study treatments (75/2.5 dose vs placebo, 37.5/2.5 dose vs placebo, and 75/2.5 dose vs 37.5/2.5 dose) with 95% confidence intervals and respective p-values (for null hypothesis).

Descriptive statistic of the proportion, with 95% CI, of participants alert and not sleepy will be presented by study treatment separately in the same table as the model. Number and percentages of participants with the individual score values (1-9) will be given by study treatment. A by-participant listing of the KSS scores will be given.

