7.2 Safety Assessments

- Planned time points for all safety assessments are provided in the SoA.
- Safety monitoring will be guided by the established safety profiles of atomoxetine and
 oxybutynin, and by Phase 1 and 2 safety data for the combination. Safety assessments will
 include physical examinations, measurement of vital signs, monitoring and recording of AEs,
 SAEs, and pregnancies, recording of study or treatment discontinuations. Effects on OSA and
 sleep parameters (e.g., sleep time and sleep stages) will also be monitored by PSG.
- Adverse events of special interest include effects on urine outflow, as both atomoxetine and oxybutynin are associated with urinary retention. Effects of atomoxetine on heart rate and blood pressure are expected to be modest, as indicated by the initial data described above, and will also be monitored. Participants with serious cardiac abnormalities will be excluded from the study. Suicidal ideation in children and adolescents is a boxed warning for atomoxetine; however, analysis in adult patients, the target population for the proposed OSA study, did not reveal an increased risk of suicidal ideation or behavior in association with atomoxetine. Daytime sleepiness is both a potential safety outcome and efficacy outcome in OSA. Both atomoxetine and oxybutynin may be associated with somnolence, and oxybutynin is additionally associated with anticholinergic CNS effects such as memory difficulty.

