2.2.3. Tertiary Endpoints

The tertiary efficacy endpoints are as follows:

- Karolinska Sleepiness Scale (KSS) score
- Sleep Quality VAS
- OSA endotype endpoints (Vpassive, Vactive, Muscle Compensation, Loop Gain)
- PSG sleep and arousal parameters
 - Sleep stages distribution and percentage of total sleep time (TST) in the various sleep stages
 - Sleep Efficiency (SE)
 - Wake After Sleep Onset (WASO)
 - Number of Awakenings (NAW)
 - Sleep Onset Latency (SOL)
 - Percentage of total sleep time (TST) spent in sleep stage N1 (Stage N1%)
 - Percentage of TST spent in sleep stage N2 (Stage N2%)
 - Percentage of TST spent in sleep stage N3 (Stage N3%)
 - Percentage of TST spent in sleep stage R (Stage R%)
 - Snoring index
 - Arousal indices (respiratory and spontaneous)
 - Fraction of hypopneas
- Alternate measures of AHI, ODI and HB
 - AHI(4%) in non-rapid eye movement (NREM) sleep
 - AHI(4%) in rapid eye movement (REM) sleep
 - AHI(4%) adjusted for position
 - AHI(3% or arousal)
 - HB(3% or arousals)
 - HB(Total)
 - ODI(3%)

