6.3.2. Sleep Quality VAS

A repeated measures model (see Section 4.7) will be used to model Sleep Quality VAS total score. Model based LS mean estimates will be provided for the following:

- mean score by study treatment (75/2.5 dose, 37.5/2.5 dose, placebo),

- difference in mean score between study treatments (75/2.5 dose vs placebo, 37.5/2.5 dose vs placebo, and 75/2.5 dose vs 37.5/2.5 dose) with 95% confidence intervals and respective p-values (for null hypothesis).

Summary statistics of Sleep Quality VAS total score by study treatment and a by-participant listing will also be provided.

6.3.3. PSG sleep and arousal parameters and alternate measures of AHI, ODI, and HB

Descriptive statistics for the reported value and change from baseline by study treatment will be reported for sleep stages distribution and percentage of time in the various sleep stages (SE, WASO, NAW, SOL, Stage N1%, Stage N2%, Stage N3%, Stage R%). A 95% confidence interval will be included for the change from baseline.

Snoring index, arousal indices (respiratory and spontaneous), fraction of hypopneas (see below) and alternate measures of AHI, ODI, and HB (AHI[4%]: in NREM sleep, in REM sleep, AHI adjusted for position [see below]; AHI[3% or arousal]; HB[3% or arousal]; HB[Total]; ODI[3%]) and will have results provided similar to Section 6.1 (including the model of change from baseline and the descriptive statistics).

Additional clarifying details for the analysis of some of these endpoints is as follows:

- Fraction of hypopneas will be calculated by using the number of hypopneas divided by the total number of apneas plus hypopneas.
- AHI adjusted for position: An additional covariate of % time supine (%TS) will be added to the repeated measures model for AHI(4%).

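### KSS is named as a score endpoint, but treatments are compared only through two dichotomies; a model of the score itself should be added

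*SAP*

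**What the plan says.** SAP 2.2.3 (Tertiary Endpoints) names the endpoint as "Karolinska Sleepiness Scale (KSS) score", with no responder definition. The Endpoints table in Protocol Section 3 lists "Karolinska sleepiness scale" as exploratory, with no cut-point.

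SAP 6.3.1 then sets out the analysis: "Two separate repeated measure models (see section 4.7) will be used to model the probability of being alert (KSS score ≤ 3", and in the second model the probability "of not being sleepy (KSS score ≤ 5". For both, "A logit link with binomial distribution will be employed", and the output is odds ratios for the three treatment pairs with 95% CIs and p-values. The scale itself is only described: "Number and percentages of participants with the individual score values (1-9) will be given by study treatment", with a by-participant listing. Neither cut is justified, and nothing says how to read the result if the two models disagree.

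The other two morning assessments are handled differently. For the VAS (SAP 6.3.2), "A repeated measures model (see Section 4.7) will be used to model Sleep Quality VAS total score". DSST (SAP 7.5) is modelled as the log of the number correct.

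On the role of sleepiness, Protocol 7.2 says: "Daytime sleepiness is both a potential safety outcome and efficacy outcome in OSA". The same section notes that both components may be associated with somnolence.

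**The concern.** The endpoint as named and the endpoint as compared are not the same quantity. A nine-level scale is reduced to two yes/no variables before any comparison. A change from 4 to 5, or from 6 to 8, then counts as no change in both models.

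Two things are lost. One is precision, in a crossover of 30 with up to about 20% dropout. The other is an interpretable estimate. Two odds ratios do not tell a reader how many KSS points of next-day sleepiness the data are compatible with, whereas a mean difference with a confidence interval does. KSS is also the only self-rated sleepiness measure collected after each treatment, and 6.3.1 is the only place where treatments are compared on it.

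**Working it through.** **The plan's own figure.** There is none for KSS. The only power statement (Protocol 8.1, SAP 9) concerns hypoxic burden and has no bearing here.

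**Inputs from the documents.** 30 participants; discontinuation below 20%, so 30 × 0.8 = 24 completers at the limit; scale 1-9; cuts at 3 and 5; two-sided 0.05.

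**Inputs assumed, because the documents give none.** KSS SD 2 on any one night; within-participant correlation 0.5; true shift 1 point towards sleepiness; placebo mean 3.5 to 4.5.

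**Step 1: power on the score.**
- SD of the paired difference = SD × √(2(1 − ρ)) = 2 × √(2 × 0.5) = 2.
- Noncentrality = shift ÷ (SD of difference ÷ √n). For n=24: 1 ÷ (2 ÷ 4.899) = 2.45. For n=30: 1 ÷ (2 ÷ 5.477) = 2.74.
- The noncentral t distribution gives 65% and 75%. Rounding to whole scores adds about 1/12 to each night's variance, so the SD of the difference becomes √(4 + 2/12) = 2.04 and power becomes 63% and 74%. Simulation of rounded scores held within 1-9 gives about 62% and 73%.

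**Step 2: power on the cuts.** In the same simulated data, each dichotomy was tested with a mid-p McNemar test.

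| Completers | Score (paired t) | Each cut alone | Either cut significant |
|---|---|---|---|
| 24 | about 62% | 24-32% | about 46% |
| 30 | about 73% | 31-40% | about 56% |

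The power retained by one cut is 24/62 = 0.39 to 32/62 = 0.52 at n=24, and 31/73 = 0.42 to 40/73 = 0.55 at n=30. If either cut counts, it is 46/62 = 0.74 and 56/73 = 0.77, a loss of about a quarter. With two tests the chance of at least one false positive is about 5-8%.

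**Why a cut is weak.** At n=24 only about 6.5 to 8.5 participants differ between two treatments on a given cut. About a third of those whose score changes cross neither cut. With 7 discordant participants split 6 to 1, the mid-p value is 2 × 8/128 − 7/128 = 9/128 = 0.07, which is not significant.

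**Step 3: wider assumptions.** Placebo mean 3.5, 4.5 or 5.5; SD 1.5 or 2; correlation 0.3, 0.5 or 0.7; n=24 or 30; effect sized so that the score has 72-80% power. The same participant, period and treatment model was fitted to the score and to each dichotomy.
- The ≤3 cut keeps 0.26-0.71 of the score's power and the ≤5 cut 0.27-0.70, a loss of roughly 30-75% per cut.
- Counting either cut keeps 0.65-0.91, with about 9% false positives.

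**Step 4: a logistic check.** A bias-reduced logistic GEE (200 runs, placebo mean 4.5, SD 2, correlation 0.5) gave these results:
- n=24, effect about 1.2 points: score 73%, ≤3 21%, ≤5 41%, either 52%.
- n=30, effect 1.05 points: score 82%, ≤3 31%, ≤5 43%, either 57%.

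The direction is the same. The planned GLIMMIX models were not run, so all of these are stand-ins.

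**The case against.** The case for leaving 6.3.1 alone has weight. Naming an endpoint as a score does not fix its summary measure. Both cuts are pre-specified and carry a plain meaning, and SAP 6.2.5 takes the same responder approach. The VAS is a different kind of scale, so its linear model creates no obligation, and a linear model of KSS treats ordinal categories as equally spaced. KSS is exploratory and is not in the Section 4.5 test list. All of this stands and limits the point to an improvement, but it does not supply a between-treatment estimate on the scale that the endpoint names.

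A reader might also infer four stronger things, which the documents do not support:

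- **That the plan halves the power.** The documents contain no KSS input from which that could follow. Under the assumptions above it roughly describes one cut alone, but the SAP runs two. Part of the gap is also a size difference: under the null the mid-p McNemar test rejected in only 2.1-4.5% of runs per cut, against about 5% for the t-test.
- **That a shift on one side of a cut would go unseen.** It would not. SAP 6.3.1 shows counts at every score by treatment and a listing. Such a shift would be displayed but not estimated or tested.
- **That the logistic models would be unstable.** This was not computed, and Section 4.7 already names a Cholesky parametrisation for logistic models and for convergence failure.
- **That the safety assessment of next-day sleepiness rests on this analysis.** KSS is not among the safety endpoints in either document. DSST has its own model with ratios and CIs (SAP 7.5), and somnolence would appear in the adverse event tables by treatment and intensity (SAP 7.2.5). Nothing says that a null KSS result would be read as reassurance, and at 62-73% power a null on the score would be limited reassurance too.

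**Conclusion.** The concern holds as a modest one. The SAP names the KSS score as an endpoint but estimates no treatment difference on it. The structural part comes straight from SAP 2.2.3 and 6.3.1 and needs no assumption.

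The size does need assumptions. In the central scenario power falls from about 62% to 24-32% for each cut alone, and to about 46% if either counts, at 24 completers. At 30 it falls from 73% to 31-40% and 56%. Outside that scenario the loss for a single cut runs from roughly 30% to 75%, depending mainly on where the placebo scores lie relative to the cut. These figures rest on assumed KSS values and on simple tests standing in for the planned models.

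No confirmatory conclusion is affected. What is missing is a more precise and more readable estimate of next-day sleepiness from data the trial already collects.

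**What to change.** In SAP 6.3.1, add the Section 4.7 repeated measures model on the KSS score with its default identity link and Gaussian distribution. Report LS means by treatment and the three treatment differences with 95% CIs, laid out as in 6.3.2. The model must use the score and not change from baseline, because the Schedule of Activities has KSS only after the three crossover nights.

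An ordinal model would serve equally well. The SAP would then have to state its link and covariance, which Section 4.7 does not give.

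Keep the ≤3 and ≤5 models as supportive analyses, and say that the score analysis is the main KSS comparison, so that disagreement between the two cuts needs no separate rule.

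The cost is one extra model and table, with no new data. The drawback of the linear version is that it treats an ordinal scale as numeric; the tabulated 1-9 distribution lets a reader judge whether that matters.
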